
An analysis will be performed during the study after <math>\sim 80</math> subjects have completed their Month 3 visit. The change from Baseline to 3 months in 1-hr pad weight will be analyzed, to help plan future studies. Viveve team members, subjects, and study site personnel working on the study will remain blinded to individual subject's treatment groups; unblinding of the individual subject's treatment group will only occur at final database lock for Viveve team members, subjects, and study site personnel working on the study. Since this analysis during the study will be analyzing CFB to 3 months post-baseline in 1-hr pad weight, which is not the primary efficacy endpoint for this study, no statistical adjustment is planned for the final significance level (<math>\alpha = 0.05</math>) for the primary efficacy endpoint.
	
Subject Populations	

The Full Analysis Set (FAS) includes all randomized subjects and is also known as the intention-to-treat (ITT) population. The FAS will be used for all efficacy analyses.
	

The Modified ITT (mITT) includes all randomized subjects who are treated and completes the study. The mITT will be used for confirmatory analysis of efficacy endpoints.
	

The Safety Population (SP) includes all randomized subjects in whom the treatment procedure is started, regardless of if the procedure is completed. The SP will be used for all safety summaries.
	
Primary Efficacy Analysis	

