      - The first set of 100 pulses is applied to the area just behind the hymenal ring using the quadrant approach. Each quadrant is treated with five consecutive passes of five locations of pulses for a total of 25 pulses per quadrant. The pulses are applied in a clockwise fashion with an overlap of  $\sim$ 0.5 cm. Once a quadrant is fully treated with 25 pulses the next quadrant is treated until all four quadrants are treated.
    - **Position 2:** 2-4 cm beyond hymenal ring (10 pulses)
      - **Treatment tip placement beyond hymenal ring:** proximal edge 2 cm, distal edge 4 cm
      - The treatment tip will then be positioned with the proximal edge of the treatment tip window  $\sim$ 2 cm behind the hymenal ring. Five pulses are applied directly to the right of the urethra and five pulses are applied directly to the left of the urethra.
      - The first treatment tip will be removed from the handpiece and replaced by the second treatment tip.
  - Second treatment tip:
    - **Position 3:** 1-3 cm beyond hymenal ring (100 pulses), *Position 3 is  $\sim$ 1 cm overlapped with Position 1*
      - **Treatment tip placement beyond hymenal ring:** proximal edge 1 cm, distal edge 3 cm (there should be  $\sim$ 1 cm overlap between Position 1 and Position 3)
      - The second set of 100 pulses is applied in a similar fashion to the first set but at  $\sim$ 1 cm deeper than Position 1. This provides an  $\sim$ 1 cm overlap of treatment pulses.
    - **Position 4:** 3-5 cm beyond hymenal ring (10 pulses), *Position 4 is  $\sim$ 1 cm overlapped with Position 2*
      - **Treatment tip placement beyond hymenal ring:** proximal edge 3 cm, distal edge 5 cm (there should be  $\sim$ 1 cm overlap between Position 2 and Position 4)
      - The fourth depth of treatment is applied in a similar fashion to the second pass but with the proximal edge of the treatment window positioned  $\sim$ 3 cm behind the hymenal ring.

The treatment is completed when a total of 220 pulses have been applied. Subjects receiving <200 pulses will be considered an incomplete treatment, and a protocol deviation will be generated. These subjects will be asked to continue in the study; however, for the formal analyses, these subjects will only be included in the safety analysis, not in the efficacy analysis.

In the event the subject experiences pain or discomfort, the procedure may be stopped temporarily, allowing the subject to relax and adjust.

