### 10.2 ANALYSIS POPULATIONS

The Full Analysis Set (FAS) includes all randomized subjects and is also known as the intention-to-treat (ITT) population. The FAS will be used for all efficacy analyses.

The Modified ITT (mITT) includes all randomized subjects who are treated and completes the study. The mITT will be used for confirmatory analysis of efficacy endpoints.

The Safety Population (SP) includes all randomized subjects in whom the treatment procedure is started, regardless of if the procedure is completed. The SP will be used for all of the safety summaries.

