### 10.5 EFFICACY ANALYSIS

#### 10.5.1 Primary Efficacy Endpoint Analysis

The primary efficacy endpoint for this study is CFB to 6 months post-treatment in 1-hr pad weight. Analysis of covariance (ANCOVA) with treatment group, study site and Baseline 1-hr pad weight as independent variables, will be used to analyze the primary efficacy endpoint. The FAS will be used, with subjects included in their randomized treatment group regardless of the treatment they actually received. The Baseline 1-hr pad weight is defined as the 1-hr pad weight at the Screening Visit. Missing values for the 6 month 1-hr pad weight will be imputed using a multiple imputation method that assumes the data are missing at random. Imputed datasets will be analyzed using an ANCOVA model with treatment group, study site, and Baseline 1-hr pad weight as independent variables.

Approximately 100 imputed datasets will be created, with results from the analysis of each imputed dataset combined using Rubin's method. The adjusted mean change and standard error (SE) will be provided for both treatment groups, along with the difference in adjusted mean change, its 95% confidence interval (CI) and associated p-value. The adjusted mean changes for each study site will also be provided.

A confirmatory analysis of the primary efficacy endpoint will be performed using the FAS and same ANCOVA as the primary analysis, but using only observed case data (no imputation will be performed for missing data). A second confirmatory analysis of the primary efficacy endpoint will be performed using the mITT, using only observed case data.

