## 2. INTRODUCTION

Stress urinary incontinence (SUI) is a major challenge for many women particularly those who have experienced child birth or are menopausal. Upwards of 55% of women with a previous vaginal delivery may exhibit signs and symptoms of SUI (Tahtinen 2016). The overarching effects of SUI impact a women's health and quality of life and have been shown to result in depression, social stigma and lack of self-confidence. The need to use an external pad to absorb urine leakage from even normal daily activities such as laughing, or coughing is unsatisfactory and can be extremely inconvenient, and often embarrassing for women.

Currently available treatment options for women are limited. Pelvic floor exercises (such as Kegels) offer some benefit to a percentage of women but compliance and sustained benefit can be issues. More aggressive approaches to manage SUI include pelvic surgery, slings and mesh. These invasive options involve more risk and recovery time and are a last resort for many patients.

The gap between conservative and invasive treatment options for SUI represents an opportunity to address an enormous unmet healthcare need for women. Minimally invasive treatments for SUI would be a highly appealing solution provided they offered a safe, consistent improvement in symptoms without significant time commitment or recovery. Any effective treatment would represent a major advance in women's health.

The Viveve Procedure, SUI protocol, offers a non-surgical alternative to traditional surgery using non-ablative, monopolar radiofrequency (RF) energy to improve SUI. It induces a mild, controlled reaction in the submucosal tissues that stimulates the body to restore collagen, thereby remodeling the tissue without causing scarring.

This Statistical Analysis Plan describes the analyses planned for protocol VI-17-01 version dated 23October2018, to demonstrate that the active treatment (i.e., Viveve Treatment, SUI protocol) is superior to the sham treatment.

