##### 5.1.1.2 Modified Intent-to-Treat Population

The Modified ITT (mITT) includes all randomized subjects who are treated and complete the study. The mITT will be used for confirmatory analysis of efficacy endpoints.

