### 5.2. Statistical Analysis of Primary Measures

The primary efficacy endpoint for this study is CFB to 6 months post-treatment in 1-hr pad weight. Analysis of covariance (ANCOVA) with treatment group, study site and Baseline 1-hr pad weight as independent variables, will be used to analyze the primary efficacy endpoint. The FAS will be used, with subjects included in their randomized treatment group regardless of the treatment they actually received. The Baseline 1-hr pad weight is defined as the 1-hr pad weight at the Screening Visit. Missing values for the 6 month 1-hr pad weight will be imputed using a multiple imputation method that assumes the data are missing at random. Imputed datasets will be analyzed using an ANCOVA model with treatment group, study site, and Baseline 1-hr pad weight as independent variables. Approximately 100 imputed datasets will be created, with results from the analysis of each imputed dataset combined using Rubin's method. The adjusted mean change (AMC) and standard error (SE) will be provided for both treatment groups, along with the difference in AMC, its 95% confidence interval (CI) and associated p-value. The AMCs for each study site will also be provided.

Assuming the data is missing at random and the pattern of missing data is monotone the following generalized code will be used.

```
PROC MI data=Widedataset nopolish out=outmi seed=501213 NIMPUTE = 100;
class Treatment Site; /* */
monotone reg (CFB /details);
var Treatment Site V1PW CFB ;
run;

/* NOTE: Although currently shown below together in one model PROC MIXED may
need to be run twice once for the lsmeans and once for the differences, in order to
work well in MIANALYZE. */

PROC MIXED data=outmi;
class Treat Site;
model CFB = Treatment V1PW Site /solution covb;
lsmeans treat/ pdiff cl;
by _imputation_;
ods output solutionf=mxparms CovB=mxcovb lsmeans=lsmeans_ds(drop=effect)
diffs=pdiff ;
run;
```

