#### **5.5. Mid-study Analysis**

A prospective analysis was to be performed after ~80 subjects have completed their 3-month visit. However, prior to this time, the sponsor decided not to perform the Mid-Study Analysis in order to maintain the LIBERATE International study integrity. The Mid-Study Analysis could potentially impact study data integrity.

When the last subject has completed her 6-month visit, the final database lock will occur for all data for all subjects. At this time, the database will be fully unblinded and all protocol-defined analyses and summaries will occur.

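### Protocol 4.2.4 drops randomized women with fewer than 200 pulses from efficacy, while the protocol's statistics sections and the SAP analyse everyone randomized

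*Protocol*

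**What the plan says.** Protocol 4.2.4 (Randomization Visit) classes fewer than 200 of the 220 planned pulses as an incomplete treatment and a protocol deviation. It asks these women to stay in the study and then adds that "for the formal analyses, these subjects will only be included in the safety analysis, not in the efficacy analysis".

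The other sections set a different rule:

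- Protocol 10.2: "The Full Analysis Set (FAS) includes all randomized subjects and is also known as the intention-to-treat (ITT) population".
- Synopsis, Subject Populations, repeated in Protocol 10.2 and SAP 5.1.1.1: "The FAS will be used for all efficacy analyses".
- Protocol 10.5.1, on the primary endpoint: "The FAS will be used, with subjects included in their randomized treatment group regardless of the treatment they actually received". SAP 5.2 uses the same set, "with subjects included in their randomized treatment group regardless of the treatment they actually received".
- SAP 5.1.1.2: "The Modified ITT (mITT) includes all randomized subjects who are treated and complete the study". Neither document ties being treated to a number of pulses.
- SAP 5.1.1.3: the Safety Population needs only that the procedure was started.

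The SAP mentions pulse counts once, in 5.11, as an item to be listed. Neither document says which text prevails.

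**The concern.** A randomized woman who receives, say, 150 pulses and returns at Month 6 is in the primary analysis under 10.2 and 10.5.1 and out of it under 4.2.4. Two competent programmers could build different primary datasets. It is also unclear whether her observed Month 6 pad weight would be used, discarded, or set to missing and multiply imputed.

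The exclusion turns on something that happens after randomization. Section 4.2.4 gives no cause for a low pulse count, but it and 8.5.3 both describe stopping because the procedure cannot be tolerated. If such stopping differs by arm and the women who stop do worse, removing them biases the comparison, in favour of active treatment if they are mainly active subjects. The two arms receive different energy doses, so a difference is possible. The documents do not show one, and Protocol 8.1 states that the two tips are indistinguishable in use to subject and investigator.

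The analysis affected is the primary one, the only test for which Protocol 10.8 and SAP 5.9 claim control of Type 1 error.

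**Working it through.** **1. The text, for one woman with fewer than 200 pulses who completes Month 6**

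| Source | In the efficacy analysis? |
|---|---|
| Protocol 4.2.4 | No |
| Synopsis; Protocol 10.2, 10.5.1 (FAS) | Yes, as randomized |
| SAP 5.1.1.1, 5.2 (FAS) | Yes, as randomized |
| mITT (Protocol 10.2, SAP 5.1.1.2) | Yes, if a partial procedure counts as treated; not stated |

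The mITT cannot be what 4.2.4 means. It has no pulse threshold, it also drops non-completers, and it serves only the supportive analyses that the plan calls confirmatory.

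**2. The plan's own power figure**

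Inputs from Protocol 10.1: 66 and 33 subjects, two-sided 5% t-test, reductions of 50% and 30% (difference 20 points), SD 28 or 33.

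Standard error = SD × √(1/66 + 1/33): 5.97 at SD 28 and 7.04 at SD 33. Noncentrality = 20/SE: 3.35 and 2.84. Noncentral-t power on 97 degrees of freedom is 91.3% and 80.4%, against the stated 90% and 80%. The figures reproduce. They count all 99 randomized subjects, which fits the FAS rule and not the exclusion in 4.2.4.

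**3. Power if 4.2.4 were applied**

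The share of incomplete treatments is an assumption. If it were equal in both arms, with the difference unchanged:

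| Share excluded | SD 28 | SD 33 |
|---|---|---|
| 2% | 90.7% | 79.6% |
| 5% | 89.8% | 78.3% |
| 10% | 88.2% | 76.0% |
| 15% | 86.3% | 73.6% |

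**4. Bias if 4.2.4 were applied**

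Assume k active and no sham subjects are excluded, with the randomized active mean held at 50% and the excluded women improving by r%. Then

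inflation = k(50 − r)/(66 − k).

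| k | r = 30 | r = 0 |
|---|---|---|
| 3 | 60/63 = 0.95 | 150/63 = 2.38 |
| 5 | 100/61 = 1.64 | 250/61 = 4.10 |
| 7 | 140/59 = 2.37 | 350/59 = 5.93 |

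Against the planned 20 points this is 5% to 30%. If the 50% is instead assigned to the women fully treated, the formula is k(50 − r)/66 and the range is 0.91 to 5.30 points.

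Cases that go the other way, with shortfall d relative to the arm mean:

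- The excluded women respond like the rest of their arm (d = 0): bias 0.
- Both arms lose the same share with the same shortfall, for example 6 of 66 and 3 of 33: 6d/60 − 3d/30 = 0.
- Only 3 of 33 sham subjects are excluded, 20 points worse: −(3 × 20)/30 = −2.0 points.

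**5. Type 1 error for an inert device**

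SD 28, active-only exclusion, bias = kd/(66 − k), noncentral t:

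| k | d | Bias | Two-sided rejection rate |
|---|---|---|---|
| any | 0 | 0 | 5.0% |
| 3 | 20 | 60/63 = 0.95 | 5.3% |
| 3 | 30 | 90/63 = 1.43 | 5.6% |
| 7 | 20 | 140/59 = 2.37 | 6.7% |
| 7 | 30 | 210/59 = 3.56 | 8.9% |

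Sections 3 to 5 use percent reduction and an unadjusted t-test, as the plan's own sample-size text does. The primary model is an ANCOVA on change in pad weight with multiple imputation, so these points do not translate directly into the primary estimate.

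**The case against.** The governing text is nearly unanimous. The synopsis, both protocol statistics sections and the later SAP give one rule, and 4.2.4 is a single sentence inside a device-procedure section. That no population implements it suggests leftover wording. An analyst who follows the SAP would keep these women. SAP 5.11 also fixes population membership before unblinding, so nobody could choose between the rules after seeing results. All of this stands, and it is why the point is not rated higher. Blind placement does not, however, make an exclusion based on a post-randomization event unbiased.

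It can also be argued that the SAP's silence proves little. The SAP does declare that "This Statistical Analysis Plan describes the analyses planned for protocol VI-17-01 version dated 23October2018", and it openly records one departure: "the sponsor decided not to perform the Mid-Study Analysis in order to maintain the LIBERATE International study integrity". But it makes other changes without comment; for example, it omits the summary of deaths and of withdrawals due to adverse events that Protocol 10.6 promises. This is fair: silence does not show that the exclusion survives. Nor does it show that the exclusion was withdrawn. The sentence in 4.2.4 is written as a rule for the formal analyses, and a reader could hold that the specific rule overrides the general one.

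Finally, the sizes rest on assumed stop rates, responses and arm imbalance, and with few exclusions the effect on Type 1 error is slight. That is correct, and the conclusion does not depend on them.

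**Conclusion.** The concern holds and should be fixed. Protocol 4.2.4 contradicts the plan's definition and use of the FAS, and neither document resolves the conflict. This rests on the text alone.

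The size in practice is unknown, because no rate of incomplete treatment is given. Under the assumptions shown, with only active subjects excluded and improving less than their arm, the planned 20-point difference would be overstated by about 1 to 6 points. It would be unchanged or understated under other, equally undocumented, patterns. Loss of power is the smaller issue: with 5% excluded from both arms it falls from 91.3% to 89.8% at SD 28. The SAP's all-randomized rule is the sound one and is already the sponsor's majority text.

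**What to change.** - **Protocol 4.2.4:** strike the efficacy exclusion. State that women with fewer than 200 pulses stay in the FAS in their randomized arm for all efficacy analyses and have the scheduled Month 3 and Month 6 efficacy assessments. Section 4.2.4 describes their follow-up as being for safety, whereas 8.5.3 has no such limit; align the two so that sites do not omit the pad tests.
- **SAP 5.1.1.1:** add one sentence saying that no pulse-count exclusion applies to the FAS and that this supersedes Protocol 4.2.4.
- **SAP 5.1.1.2:** say whether a partly treated subject counts as treated for the mITT.
- Confine any analysis restricted to completed treatments to a named supportive set.

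The cost is a short protocol correction, two clarifying sentences in the SAP before subjects are placed into populations, and a reminder to sites. These women are already asked to continue, and Table 1 and sections 4.2.6 and 4.2.7 schedule the pad tests without exemption, so no visits are added. If a site has read the safety wording as excusing the pad tests, values already missed cannot be recovered and fall under the planned imputation. No pulse threshold or stopping rule is changed.

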#### **4.2.5 Telephone Call (Day 10)**

The investigator, or designee, will contact each subject via telephone 10 days ( $\pm$  3 days) after the treatment procedure to assess each subject's health status. During the call, study site staff will assess adverse events and concomitant therapies and medications. The investigator, or designee, will request that the subject comes to Visit 4 with a full bladder.

#### **4.2.6 Visit 4 (Month 3)**

The following procedures will be carried out at Visit 4 (Month 3):

- Concomitant therapy and medications assessment
- Adverse events assessment
- Vital signs assessment
- Collection and scoring of 3-day bladder voiding diary
- 1-hr pad weight test
- Subjects will be asked to fill out the following questionnaires:
  - UDI-6
  - ICIQ-UI-SF
  - I-QOL
  - FSFI
- Distribute and re-train subject on 3-day bladder voiding diary
- Request that the subject comes to Visit 5 with a full bladder

#### **4.2.7 Visit 5 (Month 6)**

The following procedures will be carried out at Visit 5 (Month 6):

- Concomitant therapy and medications assessment
- Adverse events assessment
- Vital signs assessment
- Collection and scoring of 3-day bladder voiding diary
- Weight measurement
- Physical exam, including pelvic exam
- Urine pregnancy test will be collected and results recorded
- 1-hr pad weight test
- 24-hr pad weight test
- Subjects will be asked to fill out the following questionnaires:
  - UDI-6
  - ICIQ-UI-SF
  - I-QOL
  - FSFI

#### **4.2.8 Adverse Events and Concomitant Therapies and Medications**

##### **4.2.8.1 Adverse Events**

All adverse events (AEs) will be collected from the date the subject signs the Informed Consent Form. Subjects will be assessed for AEs at each study contact point or visit. Details of the AE, including date of onset/resolution, severity, resultant therapies/medications used to treat, and assessment of relatedness, by the Investigator, to the procedure will be collected from the investigative sites for each AE. Additionally, each AE will be assessed by the medical monitor for relatedness.

#### **4.2.8.2 Concomitant Therapies/Interventions**

All concomitant therapies and medications will be tracked for each subject from the date of screening until her exit from the study. Additionally, interventions that she undergoes (e.g., surgeries, additional therapies) throughout her participation in the study will be recorded.

#### **4.2.9 Study Exit/Study Completion**

Each subject will be exited from the study after completion of her 6-month follow-up visit (or earlier if the subject withdraws consent prior to the completion of the 6-month follow-up).

### **5 STUDY POPULATION**

Subjects must meet all of the inclusion criteria and none of the exclusion criteria to be considered eligible to participate in the study.

#### **5.1 SUBJECT INCLUSION CRITERIA**

At the Screening Visit, a subject must meet the following criteria to participate in this study:

- I.1 Able to understand and has voluntarily signed and dated the informed consent form (ICF) prior to initiation of any screening or study-specific procedures.
- I.2 Willing to comply with study requirements and instructions.
- I.3 Documented diagnosis of stress urinary incontinence with urethral hypermobility as determined by Q-tip test. If there are mixed symptoms there must be a predominant stress component as determined by investigator or designee.
- I.4 Pre-menopausal females,  $\geq 18$  years of age. Premenopausal is defined as a woman who has had menstrual cycles over the previous 12 months. If menstrual cycles cannot be established, premenopausal can be defined as FSH levels  $<30.0$  mIU/mL.
- I.5 Subjects with a BMI of  $\leq 35$  kg/m^2.
- I.6 Normal, or abnormal but not clinically significant (as determined by the investigator), physical, pelvic and neurologic exam at the Screening visit.
- I.7 Negative pregnancy test at Screening and Randomization visit.

Subject uses an acceptable form of birth control started  $\geq 3$  months prior to screening. Acceptable forms of birth control include: abstinence from heterosexual vaginal intercourse, hysterectomy, double tubal ligation, vasectomy, double barrier contraception, intrauterine device or hormonal contraceptive. Rhythm and withdrawal are not considered acceptable forms of contraception.

- I.8 Patient-reported or documented diagnosis of SUI symptoms for  $> 6$  months.
- I.9 Positive Bladder Stress Test at Screening.
- I.10 1-hr pad weight at Baseline with a 5 to 50 g net increase from the pre-test pad weight.
- I.11 Subjects must complete 3 days in the 3-day voiding diary during the 3 consecutive days prior to the Screening Visit, AND subjects must report a minimum of 1 incontinence episode per day as determined in the 3-day voiding diary.

